## 2.2 QR-110 for the Treatment of Leber's Congenital Amaurosis due to *CEP290* p.Cys998X Mutation

The primary goal of the development plan for QR-110 is to provide a treatment to overcome the genetic defect in patients with at least one *CEP290* allele containing the p.Cys998X mutation.

QR-110 is an AON designed as a disease modifying therapy for LCA due to the *CEP290* p.Cys998X mutation. QR-110 targets the splicing mutation of the *CEP290* protein through a mechanism of RNA modulation that skips the inclusion of the cryptic exon-X. The exclusion of this cryptic exon results in restoration of the open reading frame of *CEP290* and excludes the premature stop codon present in exon-X.

## 2.2.2 Clinical Experience

No clinical studies have been conducted with QR-110 Solution for IVT Injection.

## 2.3 Study Rationale

There are currently no approved therapies for the treatment of LCA due to the *CEP290* p.Cys998X mutation and a large unmet medical need exists. QR-110 is designed to target the splicing mutation in the *CEP290* protein. The hybridization of the QR-110 oligonucleotide modulates the RNA splicing process, blocking access to the active cryptic splice site and restoring preference for the wild-type splice sites, skipping the inclusion of the cryptic exon-X in *CEP290*, and resulting in a functional *CEP290* protein.

This first-in-human study of QR-110 is an open-label, multiple dose, dose escalation study to evaluate the safety and tolerability of QR-110 administered via IVT injection in subjects with LCA due to the *CEP290* p.Cys998X mutation. It is anticipated that repair of the splicing defect may be possible in patients with preservation of at least detectable ONL. Patients with LCA due to the *CEP290* p.Cys998X mutation exhibit progressive retinal degeneration and substantial loss of rod photoreceptors in the peripheral retina; however, sparing of foveal/macular cone photoreceptors has been observed. Such cone photoreceptor sparing is noted in some patients by the presence of an almost normal retinal ONL thickness at the foveal region and retained cone-specific retinal function. Importantly, age does not seem to be strictly associated with disease severity ([Cideciyan 2007](#), [Cideciyan 2011](#), [Pasadhika 2010](#)).

The phenotype of LCA due to mutations in *CEP290* is severe. However, in a cohort of Dutch patients, [Yzer et al \(2012\)](#) concluded that patients usually have a relatively normal optic disc, mild or moderate attenuation of vessels and a relatively preserved posterior pole, suggesting that anatomy is preserved. There is evidence of sparing of some photoreceptors in the macula of individuals with LCA carrying *CEP290* mutations, which may allow for therapeutic intervention.

Restoration of protein expression to wild-type levels has the potential to delay, cease, or possibly to reverse disease progression ([Chacon-Camacho 2015](#)).

### 2.3.1 Rationale for Open-label Design in Patients

Intravitreal injection is a well-established route of administration within ophthalmic indications; however, rare but potentially serious complications to IVT injections exist, including acute onset endophthalmitis, pseudo-endophthalmitis, cataract and retinal detachment. Although the risk of serious complications is small, it is well-documented ([Artunay 2009](#), [Fagan 2013](#), [Falavarjani 2013](#)). Therefore, placebo injections will not be administered in this study to preserve subject safety.

Use of sham injections to mask subjects to treatment assignment in studies of products administered via IVT injection eliminates the risk of complications due to injection in the contralateral eye. Sham injections that closely mimic the active injection can effectively mask participants to treatment assignment; however, the masking effect is less pronounced in the case where a single subject would receive both the real and sham injections, one in each of their eyes ([Glassman 2012](#)), as would be required in LCA due to the *CEP290* p.Cys998X mutation.

This study will be an open-label study and sham injections will not be used. Masking of participating subjects is of particular importance when subject effort or perception could bias evaluation of study endpoints; this is true for the assessment of subjective endpoints such as visual acuity ([Glassman 2012](#)). However, many assessments are objective tests (Pupillary Light Reflex [PLR], OCT, oculomotor instability [OCI], ERG, and infrared imaging) which are not related to subject responses. A central reading center will be used for several of the ophthalmologic assessments, including PLR, OCI, Full Field Stimulus Testing (FST), ERG, OCT and infrared imaging, which will be reviewed and interpreted by an independent masked evaluator. Mobility course scoring will also be reviewed and calculated by a masked evaluator. Furthermore, this study will evaluate safety and tolerability as the primary endpoint. Measures of safety will be monitored and severity and causality determined by the Investigator. Taken together, the risk of the introduction of bias to the determination of safety from the participant is low and sham injections will not reduce bias introduced by Investigators.

Subjects will receive QR-110 as a unilateral IVT injection in their worse eye (see [Section 4.2.1.2](#)). Treatment of the worse eye is common practice in the development of ophthalmic products ([Bainbridge 2008](#), [Ghazi 2016](#), [Jacobson 2012](#), [Maguire 2009](#)). Unilateral injection serves as an additional means to ensure safety, as visual function is driven by a subject's better eye. Unless otherwise specified, both safety and efficacy evaluations

-will be based on the assessment of the treatment eye in comparison to baseline measures and to the untreated eye (referred to hereafter as the contralateral eye). As there is no approved therapy for the treatment of LCA due to the *CEP290* p.Cys998X mutation, no suitable comparator currently exists. The contralateral eye, therefore, serves as a control and removes the biases due to the absence of a relevant comparator, or the

administration of placebo by IVT injection, which is considered unethical in this population. Assessments based on both the comparison of the treatment eye to the contralateral eye, and changes from baseline in the treatment eye will provide the strongest comparisons from which to evaluate safety and efficacy data.

## **2.4     Route of Administration, Dosage, Dosage Regimen and Treatment Period**

Intravitreal injection is a well-established route of administration within ophthalmic indications. Systemic exposure to drugs administered via IVT injection is generally low and the technique enables targeting of the product to the intraocular tissues of the eye ([AAO 2015](#)). Intravitreal injection is used in several products for the chronic treatment of ophthalmic diseases (eg, Lucentis®, Eylea™, Macugen®) and the risk of complications is low when injections are performed by trained ophthalmologists ([AAO 2015](#)).

Since IVT injections themselves carry a low risk of serious complications, independent of the product administered, dose levels to be investigated in the study are calculated to be pharmacologically efficacious doses. Evaluation of up to 3 dose levels of QR-110 is planned. Inclusion of up to 3 dose levels enables investigation of a potential dose response relationship for QR-110. Based on the chemistry of the molecule, PK data from toxicology studies, and what is known of other oligonucleotides approved for IVT injection (Macugen®, Vitravene®), systemic absorption is anticipated to be low.

Each subject will receive up to 4 doses of QR-110 at 3 month intervals and will be monitored for 3 months following their last dose of study drug. The dosing interval of 3 months and the 12-month duration of dosing is expected to be in the efficacious range for QR-110.

Administration of 4 doses has been selected to enable evaluation of the safety of repeat dosing of QR-110 and to evaluate potential efficacy parameters. The multiple dose design provides subjects with the potential opportunity for efficacy. A single dose design is not considered acceptable in this population because subjects would be exposed to the risks associated with IVT injection without the possibility of being able to derive any (sustained) benefit. To ensure subject safety in this multiple dose design, an independent Data Monitoring Committee (DMC) will review all available safety data prior to each dose escalation, prior to inclusion of pediatric subjects, and prior to the first subject receiving each subsequent dose of QR-110 (doses 2, 3, and 4). Therefore, the study consists of a single initial dose, with DMC review of cumulative study data and a positive DMC recommendation prior to continuing to each subsequent dose.

### **2.4.1     Dose Selection Rationale**

The proposed starting dose and escalation scheme for PQ-110-001 is considered conservative.

The proposed dosing regimens to be studied are as follows:

- Low dose: 160  $\mu$ g loading dose, followed by up to three 80  $\mu$ g maintenance doses
- Middle dose: 320  $\mu$ g loading dose, followed by up to three 160  $\mu$ g maintenance doses
- High dose: 500  $\mu$ g loading dose, followed by up to three 270  $\mu$ g maintenance doses

Details on the dose selection are provided in the QR-110 IB.

## 2.5 Study Population

The study drug will be administered by IVT injection which carries a risk of serious complications, making the inclusion of healthy volunteers unethical. Furthermore, QR-110 is designed to exert the specific effect of masking the cryptic splice site in patients with the *CEP290* p.Cys998X mutation, which is not present in healthy volunteers. It is, therefore, unknown if safety data obtained from healthy volunteers, would be similar to that of patients with the target mutation. Evaluation of patients with LCA due to the *CEP290* p.Cys998X mutation is therefore necessary to evaluate the safety of QR-110.

Eligible subjects will have LCA due to homozygosity or compound heterozygosity for the *CEP290* p.Cys998X mutation, residual vision and detectable ONL in the area of the macula as determined by OCT. Preservation of at least some retained photoreceptor ONL is a prerequisite for restoration of the splicing defect and consequent impact on disease. Due to severe nystagmus in many subjects with LCA due to the *CEP290* p.Cys998X mutation, it is anticipated that consistent, quantitative calculation of the volume of retained ONL across subjects may be a challenge in this population; therefore, eligibility will be determined by the existence of any detectable ONL on OCT, in the opinion of the Investigator.

Since disease severity does not seem to clearly correlate with age, inclusion of subjects in the first-in-human trial should be guided by disease status and potential for obtaining a therapeutic benefit. The high unmet medical need warrants early therapeutic intervention in those patients with sufficient preserved vision and retinal anatomy in which a major clinical benefit (restoration or improvement of vision or delay in visual loss) could potentially be expected. Therefore, treatment with QR-110 is justified in those patients with LCA due to the *CEP290* p.Cys998X mutation who present detectable ONL, irrespective of age.

### 2.5.1 Inclusion of Pediatric Subjects

Symptoms of LCA due to the *CEP290* p.Cys998X mutation occur in young pediatric patients; symptoms are usually detected before 1 year of age and patients show severe vision disturbances. Pediatric patients could benefit from treatment with a therapy for LCA due to the *CEP290* p.Cys998X mutation beginning at a very young age. Given the timing of symptom onset and substantial vision loss in young children, it is possible that early initiation of treatment may result in improved clinical outcomes for patients. While the potential to at least cease progression can

be assumed to be most beneficial to younger patients, the target patient population for the first-in-human study of QR-110 will only include pediatric patients at least 6 years of age to ensure subject safety and due to the complexity of study assessments. A staggered approach has been selected such that pediatric subjects (pediatric patients include those 6 to less than 18 years of age) will only start treatment following review of safety and tolerability data from adult subjects (adult subjects include those  $\geq 18$  years of age).

In pediatric subjects at least 6 years of age, the average volume of vitreous is similar to that of adult subjects, as referred in [Bhardwaj et al \(2013\)](#) and [Zadnik et al \(2004\)](#). Intravitreal administration of anti-Vascular Endothelial Growth Factor A agents is used to treat newborns in cases of Retinopathy of Prematurity and no issues specific to the pediatric population have been identified in connection to the IVT injection ([Mintz-Hittner 2008](#), [Nazari 2010](#)). For a product given via IVT injection, there is no evidence to suggest that the safety profile would differ in adult patients as compared to pediatric patients at least 6 years of age. Toxicity studies in juvenile animals are summarized in the QR-110 IB, Nonclinical Studies.

For the purposes of an early phase clinical study such as PQ-110-001, it is essential that participating subjects be able to complete all necessary safety and efficacy assessments; therefore, specifying a minimum age for subject eligibility is appropriate. The psychophysical tests used in low vision populations are difficult for children younger than 6 years of age to complete due to complexity and the level of focus required. In practice, the ability to complete these tests, based on the individual child and the suitability of patients of any age to complete all required assessments, will be determined by the Investigator. Furthermore, the visit frequency for this first-in-human trial will be high and visit duration lengthy due to the large number of measures required to assess safety. Therefore, the target patient population for the PQ-110-001 study will be patients at least 6 years of age who are able to complete all study assessments, in the opinion of the Investigator.

## 2.5.2 Pediatric Considerations

In accordance with best practices, the parent or legal representative of a participating pediatric subject must be informed as to procedures that are part of usual care and those specific to participation in this clinical study. Age appropriate explanations of procedures should be given to all pediatric subjects. Investigators, staff and facilities should be experienced in the care of pediatric subjects, in order to minimize pain, distress and fear. Separation of the pediatric subject from their parent or legal representative should be minimized and when necessary, the pediatric subject should be accompanied by a study staff member. Pain should be minimized (eg, use of indwelling catheters for blood draws or use of topical anesthetic agents), in accordance with local institutional practices ([Directive 2001/20/EC](#)).

### **3.0 STUDY OBJECTIVES**

#### **3.1 Primary Objective**

The primary objective of the study is to evaluate the safety and tolerability of QR-110 administered via IVT injection in subjects with LCA due to the *CEP290* p.Cys998X mutation.

#### **3.2 Secondary Objectives**

The secondary objectives of the study are:

- to evaluate the serum pharmacokinetics of QR-110 administered by IVT injection in subjects with LCA due to the *CEP290* p.Cys998X mutation
- to evaluate the efficacy of QR-110 administered by IVT injection in subjects with LCA due to the *CEP290* p.Cys998X mutation

#### **3.3 Exploratory Objective**

### **4.0 STUDY OVERVIEW**

#### **4.1 Criteria for Evaluation**

##### **4.1.1 Primary Endpoint**

- Frequency and severity of ocular AEs in the treatment and contralateral eyes

##### **4.1.2 Secondary Endpoints**

- Frequency and severity of non-ocular AEs
- Changes in ophthalmic examination findings
- Change in BCVA
- Changes in infrared imaging
- Changes in OCT findings
- Changes in safety parameters, including vital sign measurements, physical examination findings, electrocardiogram (ECG) and laboratory parameters

- Characterize the PK profile of QR-110 in serum
- Change in light sensitivity to red FST
- Change in light sensitivity to blue FST
- Change in amplitude to white PLR
- Change in latency to white PLR

#### 4.1.3      Exploratory Endpoints

The study is not designed to have sufficient statistical power to assess efficacy of QR-110 in the treatment of LCA due to the *CEP290* p.Cys998X mutation. However, changes in clinical outcome measures associated with LCA due to the *CEP290* p.Cys998X mutation will be monitored over the course of the study.

## 4.2 Study Design

The first-in-human study of QR-110 will be an open-label, multiple dose, dose escalation study to evaluate the safety and tolerability of QR-110 administered via IVT injection in subjects with LCA due to the *CEP290* p.Cys998X mutation. Subjects will be assigned to receive a specified dose level (loading dose and maintenance dose) of QR-110. No intrasubject dose escalation is planned. Up to 3 dose levels of QR-110 will be evaluated. Dose escalation decisions and initiation of dosing in pediatric subjects will be determined by the DMC and Sponsor Medical Monitor review of safety and tolerability data.

### 4.2.1 Study Plan

#### 4.2.1.1 Screening

During the screening period, subjects will be assessed according to the eligibility criteria.

Subjects who meet all eligibility criteria will be enrolled into the study. On Day 1, subjects will undergo a second set of predose baseline measures as specified in the SOE and will subsequently receive their first dose of study drug. The data obtained from these two predose measures will serve to inform the level of intrasubject variability in study assessments (see [Section 7.2](#) for more details on the screening process).

#### 4.2.1.2 Study Drug Administration

Subjects will receive study drug via unilateral IVT injection in accordance with the procedures outlined by the current international guidelines ([Avery 2014](#)) in their worse eye as defined by visual acuity (subsequently referred to as treatment eye) and will be assessed for safety and tolerability at follow up visits. If both eyes have the same visual acuity, the Investigator should determine the eye with the worse visual function, according to other measures of ophthalmic function at Screening (FST or mobility course score), as the treatment eye. If the visual function is the same per the Investigator's assessment, then the treatment eye will be determined at Investigator discretion.

Specific study drug administration procedures can be found in the Study Reference Manual.

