	
be assigned to receive a specified dose level of QR-110 (loading dose and maintenance dose) and will receive that dose throughout their participation, while they are monitored for safety. No intrasubject dose escalation is planned. Up to 3 dose levels of QR-110 will be evaluated. Dose escalation decisions and initiation of dosing in pediatric subjects (6 to <18 years of age) will be determined by the DMC and Sponsor Medical Monitor review of safety and tolerability data. The DMC and Sponsor Medical Monitor will also review all available safety data at key study time points (eg, prior to the first subject in the first adult cohort (Cohort A1) receiving each subsequent dose of study drug).
 
QR-110 will be administered by unilateral IVT injection. Each subject will receive up to 4 doses of QR-110 in their worse eye (as defined by visual acuity at Screening, subsequently referred to as treatment eye) every 3 months and will be assessed for safety and tolerability at follow up visits. If both eyes have the same visual acuity, the Investigator should determine the eye with the worse visual function as the treatment eye, according to other measures of ophthalmic function (Full-field Stimulus Testing [FST] or mobility course score). If the visual function is the same per the Investigator's assessment, then the treatment eye will be determined at Investigator discretion. No placebo nor sham injections will be administered in the contralateral eye.
 
The contralateral eye and the subject's own baseline measurements will serve as controls.
 
Subjects who do not meet stopping criteria prior to their next scheduled injection will receive their planned dose (Section 4.2.2). Subjects who meet stopping criteria will be discontinued from dosing and will be followed for safety and efficacy.
 
The DMC and/or Sponsor Medical Monitor may decide to de-escalate the dose, hold the dose (delay or skip), or discontinue study drug for an individual subject, in consultation with the Investigator. Subjects who discontinue study drug will continue to be followed for safety and efficacy.
 
An extension study, which would permit continued dosing of eligible subjects who complete PQ-110-001, is planned.
 
Dose Escalation
 
Specifics of the dose escalation plan are described in detail in Section 4.2.1.5. It is planned to dose at least 2 adults and, subsequently, at least 2 pediatric subjects at each dose level of QR-110. Up to 3 dose levels are planned across 3 dose cohorts. No intrasubject dose escalation will occur. Dosing will be staggered such that:
 

• The first 2 subjects at any dose level will be dosed at least 2 weeks apart

• At least 4 weeks of post dose safety and tolerability data on the previous cohort will be reviewed by the DMC and Sponsor Medical Monitor prior to dose escalation in subsequent subjects

• Dosing and dose escalation of pediatric cohorts will be initiated following DMC and Sponsor Medical Monitor review and will follow that of the corresponding adult cohort by at least 4 weeks

 
Following DMC and Sponsor Medical Monitor review and decision on dose escalation, the first subject at the next dose level may be dosed and the second subject at that dose level may be dosed 2 weeks later. Safety and tolerability data, including follow-up for at least 4 weeks post dose, will be reviewed by the DMC and Sponsor Medical Monitor. A complete discussion of the rules regarding timing of doses for individual subjects is presented in Section 4.2.1.5.
 
Pediatric subjects will only receive a given dose level of QR-110 following DMC and Sponsor Medical Monitor acceptance of at least 4 weeks of post dose safety and

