7.1 Study/Treatment Eye Definition and Unit of Analysis

The study eye will be the treated eye for all efficacy and safety summaries. The study eye will always be referred to as the treated eye on TLFs and is defined as the eye with the worse visual acuity at

Screening. If both eyes have the same visual acuity, the Investigator should determine the eye with the worse visual function, according to other measures of ophthalmic function (FST or mobility course score). If the visual function is the same per the Investigator's assessment, then the treated eye will be determined at Investigator discretion.

The unit of analysis for all ocular endpoints will be the eye level. All ocular endpoints will be summarized by eye and by dose group and cohort (ie, adult versus pediatric) for the treated eye and contralateral eye where appropriate. Subject level information, non-ocular AEs, medical history,-

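### When the eyes tie on Screening acuity, an unmasked Investigator settles which eye is treated, by an unordered FST-or-mobility judgement and then by free choice, where a random final pick would avoid a selection bias that is probably small

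*Protocol*

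**What the plan says.** The rule for choosing the treated eye stands in the Protocol synopsis (Study Design), Protocol 4.2.1.2 and SAP 7.1. It has three steps.

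1. The eye with the worse visual acuity is treated.
2. If acuity is equal, the Investigator determines the eye with worse function "according to other measures of ophthalmic function at Screening (FST or mobility course score), as the treatment eye". Neither test is put first, and no difference is named that would count as worse.
3. "If the visual function is the same per the Investigator's assessment, then the treatment eye will be determined at Investigator discretion". The SAP ends the same way: "then the treated eye will be determined at Investigator discretion".

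Nothing is randomised (Protocol 10.2.1, SAP 4.1). On the comparator, the synopsis says: "The contralateral eye and the subject's own baseline measurements will serve as controls". Protocol 2.3.1 names "Assessments based on both the comparison of the treatment eye to the contralateral eye", alongside change from baseline in the treated eye, as the strongest basis for judging safety and efficacy. SAP 4.1 masks the central graders of imaging, FST and mobility videos to the treated eye. That masking does not extend to the Investigator who picks the eye.

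**The concern.** With one injected eye per subject and no randomisation, naming the treated eye also names the control eye. That step should not depend on anything related to how the eyes will later fare.

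In a subject whose eyes tie on acuity, it may. The Investigator is unmasked and has already judged outer nuclear layer on OCT and clarity of the media (Protocol 5.3.1). All Screening examinations must have been performed (Protocol 8.12). If FST and mobility score disagree, either can be used. Whether function is equal is also the Investigator's call, and after that the choice is free. Picking the eye thought more likely to respond would tilt the between-eye efficacy contrasts towards benefit. Picking the eye with less to lose could tilt them, or the ocular safety comparison, the other way.

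The stated reason for treating the worse eye is that the better eye drives visual function (Protocol 2.3.1). Between eyes judged equal that reason no longer applies, so the last step can be random without giving up the protection.

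**Working it through.** **The plan's own figure.** The planned 12 subjects equal 3 dose levels × 2 age cohorts × 2 subjects (Protocol 4.2.1.4). This number rests on no power calculation, and the point does not depend on it. The documents give neither a tie rate nor any figure for a selection effect, so the size below is illustrative.

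**Inputs**
- n = 11, the number of subjects at the second interim analysis (SAP 7.6).
- m = subjects whose eye is chosen by discretion. Assumed.
- r = correlation between what guides the choice and the later between-eye difference in change. Assumed, 0.1 to 0.5.
- No drug effect, and every discretionary choice leaning the same way. Assumed.

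**Formula.** Let D be the between-eye difference in change, in SD units, and X the signal behind the choice, both standard normal with correlation r. Treating the eye that X favours gives an expected treated-minus-contralateral difference of r × E|X| = r × √(2/π) = r × 0.798 in each such subject. Averaged over all subjects:

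bias = (m/n) × r × 0.798

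- m = 2, r = 0.3: (2/11) × 0.3 × 0.798 = 0.044 SD
- m = 4, r = 0.3: (4/11) × 0.3 × 0.798 = 0.087 SD

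The standard error of a mean of 11 differences is 1/√11 = 0.302 SD, so these are 0.14 and 0.29 standard errors.

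**Range for n = 11 (SD units)**

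| m | r = 0.1 | r = 0.3 | r = 0.5 |
|---|---|---|---|
| 2 | 0.015 | 0.044 | 0.073 |
| 4 | 0.029 | 0.087 | 0.145 |
| 6 | 0.044 | 0.131 | 0.218 |
| 11 | 0.080 | 0.239 | 0.399 |

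With n = 12, the r = 0.3 values for m = 2 and 4 are 0.040 and 0.080.

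**Simulation check** (100,000 trials per setting). The mean bias agreed with the formula to within about 0.002 SD. A paired t-test at two-sided 5% would reject in 5.1% (m = 2) and 5.7% (m = 4) of trials at r = 0.3. With a random pick, the mean stayed within 0.002 SD of 0 and the error rate was 5.0% to 5.2% for every m and r. SAP 7.4 plans no such test, so the error rates only give a sense of scale.

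**Are ties plausible?** Eyes may enter at light perception (Protocol 5.3.1). SAP 14.1 scores light perception, hand movement and counting fingers as 4.0, 3.0 and 2.0 logMAR, but only where neither the ETDRS chart nor the Berkeley test gives a logMAR value. Exact ties are therefore plausible, mainly at light perception or where no logMAR value exists. Subjects who also tie on FST or mobility must be no more frequent, and may be much rarer.

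**The case against.** The best case against the point is that the free choice is the last of three steps and may never have been used. A reader might infer that a tie on acuity goes straight to discretion. It does not: FST or mobility score comes first, and Protocol 2.3.1 has masked evaluators interpreting FST and scoring the mobility course. That narrows the discretion. It does not close it, because the order of the tests and the meaning of equal function are left open, and masked grading protects measurement rather than allocation.

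Several further objections stand.
- The direction of any bias is unknown. The larger entries in the table need many discretionary choices, a strong signal and all choices leaning one way.
- The SAP is descriptive and summarises each eye separately. Inference sits in a separate SAP whose content is not visible here.
- The control eye receives no placebo or sham, so ocular adverse events already differ between eyes through the injection itself. No figure supports a material effect of tie choice on the primary endpoint.
- By-subject, by-eye listings (SAP 7.4) let a reader find acuity ties. Only the basis of the choice is missing.
- Eyes equal in function may differ in feasibility of injection, which may be assessed at Screening (Protocol 7.2). An override for a documented contraindication to injecting that eye meets this where the difference amounts to one.

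Protocol 2.3.1 also says: "The contralateral eye, therefore, serves as a control and removes the biases due to the absence of a relevant comparator". A reader might take this as a claim that selection bias is removed. The sentence concerns the lack of a comparator and the alternative of placebo injection, and does not address how the eye is chosen.

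None of this favours free choice over a random pick between eyes judged equal.

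**Conclusion.** The point holds as a modest design weakness. After a tie on Screening acuity, an unmasked Investigator settles the allocation, first by a judgement with no stated order or threshold and then freely. In those subjects the treated-versus-contralateral comparison is open to selection bias of unknown direction. With 11 subjects, r = 0.3 and 2 to 4 discretionary choices all leaning one way, the bias is about 0.04 to 0.09 SD of the between-eye difference. It is 0 in expectation with a random pick. The number of ties and r are assumptions, and the Study Reference Manual, which is not available here, may add detail on eye selection.

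The documents do not support a reading that the trial's efficacy or safety comparisons are substantially biased, or biased towards benefit. The case for change is that the weakness is avoidable at almost no cost and that the tables do not show where discretion was used.

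**What to change.** **For any further enrolment** (Protocol synopsis, 4.2.1.2; SAP 7.1): fix the order of the tie-break measures in advance. Replace the last step with a right-or-left pick from a sponsor-held random list, released once eligibility is confirmed. Allow an override only for a documented contraindication to injecting that eye.

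**For subjects already enrolled:** record whether each eye was selected by acuity, by FST or mobility, or by discretion, and add this to the baseline listing in SAP 9.2. If any eye was chosen by discretion, repeat the pooled treated and contralateral change-from-baseline and ocular adverse event summaries without those subjects. If none was, one line in the study report settles it. SAP 7.6 already speaks of all 11 subjects and of an analysis after the last subject's final visit, so this may be the only part that still applies.

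**Cost:** a short amendment, a short list, one derived variable and reruns of existing tables. No visits, tests or subjects are added. The Investigator and subject lose a free choice between eyes judged equal, and the sensitivity tables are smaller.

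**What it leaves untouched:** open-label bias in effort-dependent tests such as BCVA, and regression to the mean where the worse Screening reading picks the eye. SAP 7.3 averages Screening and Day 1 for baseline. For two truly equal eyes with independent errors, picking the worse Screening reading therefore gives a spurious treated-eye gain on that measure of 0.5 × √2 × 0.798 = 0.56 measurement-error SDs. This arises in untied subjects through acuity, and through FST or mobility wherever that step decides.
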